4.0 Study Endpoints

Outcome Measurement

Paretic Propulsion (Pp): Pp is a quantitative measure of the coordinated output of the paretic leg and is defined as the percentage of propulsion performed by the paretic leg.¹² The percentage of propulsive forces generated by the paretic leg will be calculated by dividing the total propulsive impulse (the time integral of the anterior/posterior force curve) performed by the paretic leg by the sum of the propulsive impulse done by both legs. Importantly, Pp has relatively little dependence, if any, on walking speed. Our instrumented treadmill gives us the ability to measure this quantity in much more detail than would be possible in a conventional gait laboratory because we can easily record a large number of step cycles in a single 30-second trial. Statistics will be run on the absolute deviation from normal (Deviation = $|0.5 - Pp|$).

Biomechanical Walking Testing: For instrumented treadmill assessments, participants will wear their own low-heeled shoes. A safety harness (Robertson Mountaineering) mounted to the laboratory ceiling will be worn by the participant for protection in the event of loss of balance. Each participant will be asked to walk without an assistive device or ankle-foot orthosis (although an AirCast will be allowed for medial-lateral stability if necessary). Participants will be permitted to practice treadmill walking until they feel comfortable walking without assistive devices, orthotic devices or support from the handrails. During the acclimation period, a trained staff member will offer any support the subject may require. This will continue until the participant feels comfortable enough to begin data collections. Ground reaction force data will be

low-pass filtered with a fourth-order, zero-lag digital Butterworth filter. To optimize capture of steady state data on the treadmill, subjects will walk for approximately 10 seconds to achieve steady state prior to the 30 seconds of data collection (40 seconds per trial). Two trials will be collected at the treadmill self-selected speed and two trials at the fastest comfortable speed. Biomechanical data collections will allow for secondary analyses of associated kinematic and kinetic variables (e.g. force impulse, COMa by gait cycle phase, joint moments/power/work, and joint angles). At baseline testing, post-testing, and at the beginning of *each session*, participants will walk on a 16 ft. long gait mat (GAITRite) to measure SSWS and fastest comfortable walking speed (FCWS) and other spatiotemporal parameters. Subjects will be permitted a practice trial, and then be asked to complete two trials at each speed. A safety harness mounted to the ceiling will protect the subject but will only support their body weight in the case of a loss of balance. Trained study personnel will be present for all testing sessions as needed.

Clinical Assessments: The proposed assessments are standard to most post-stroke intervention trials. As the primary aim of this proposal is to improve functional outcomes using an intervention that is clinically translatable, it is imperative to include assessments routine to clinical rehabilitation. The below measures reflect a battery of body structure and function, activity, and participation measurement to reflect a broad range of clinical assessment across the rehabilitation model (ICF) as has been previously advocated.⁵⁰ All clinical assessments will be conducted by a physical therapist evaluator blinded to group allocation (different than the training physical therapist) within the Center for Rehabilitation Research in Neurological Conditions.

- **Walking Speed:** We will assess SSWS and fastest comfortable walking speed in meters per second over a 16 foot GAITRite walkway. Mean SSWS for individuals post-stroke has been established at 0.84m/s,⁵¹ with excellent test-retest reliability (ICC=0.95 to 0.99) and interrater/intrarater reliability (0.87 to 0.88).^{3,52} Minimally Clinically Important Difference (MCID) for SSWS for stroke survivors of 0.16 m/s⁵³ allows for the clinician to set meaningful walking speed goals, while providing a classification for researchers via cut off scores: <0.4 m/s representing likely limited household ambulators, 0.4-0.8 as limited community ambulatory profile, and >0.8 m/s as community ambulators.³
- **6-Minute Walk Test (6MWT):** Timed walking tests are primarily a measure of functional capacity.⁵⁴ The 6MWT tests populations who present with little functional walking capacity and is validated against the Rivermead Mobility Index ($r=0.75$) and 10-meter walk time ($r=-0.61$).⁵⁵ The 6MWT has a high intra- and interrater reliability (ICCs = 0.82-0.95).⁵⁶ The Minimal Detectable Change (MDC) for individuals with chronic stroke is 120 feet⁵⁷ and the MCID is 113 feet.⁵⁸
- **Functional Gait Assessment (FGA):** The FGA is modified from the Dynamic Gait Index and includes 10 items to assess dynamic balance stability during gait. Each item is scored on a 4-point scale from 0 (poor) to 3 (excellent) with a maximum score of 30. The MDC is 4.2 points,⁵⁹ A score 22 or below out of 30 is predictive of falls in older adults (sensitivity and specificity each 85%).⁶⁰
- **Fugl-Meyer Assessment of Motor Function:** We will utilize the lower extremity (LE FM Assessment) portion of the assessment to characterize our participant sample. The LE FM Assessment is a measure of motor recovery post-stroke and includes measures of reflex, motor control, and coordination with a total score of 34. We will also evaluate separately the 22-point motor sub-score as well as the LE sensory portion.⁶¹
- **Stroke Impact Scale (SIS):** The SIS is a stroke-specific outcome measure that includes 59 items covering nine domains: Strength, Hand function, ADL/IADL, Mobility, Communication, Emotion, Memory and thinking, Participation/Role function, and Perceived recovery. Standard error of measurement, MDC, and MCID have been published providing clinicians key metrics to measure the clinical change and significance of the questionnaire.⁵⁹ The SIS is responsive to change at 1-3 and 1-6 months⁶² (with a greater total responsiveness than the Stroke Specific Quality of Life Scale (SRM

difference =0.36).⁵⁹ Test-retest (ICC = 0.7 to 0.92)⁶² and interrater/intrarater reliability are all excellent (ICC = 0.82 and 0.80 respectively)⁶³ with some deviations for specific domains.

- **Activities of Balance Confidence:** The ABC is a commonly used 16 item subjective measure of confidence in performing various ambulatory activities without falling or experiencing a sense of unsteadiness (falls self-efficacy). Items are graded 0-100% with higher scores representing increasing confidence in functional activities. Standard error of measurement has been published as 6.81 in chronic stroke,⁶⁴ whereas the MDC and MCID have yet to be published. A cut-off score of 81.1 can provide some evidence that the patient/subject doesn't have a history of falls.⁶⁵ Total score normative data reveals a mean (SD) of 86.3 ± 17.3 ⁶⁴ indicating that the average stroke survivor likely has some reduced confidence in their ability to perform ADLs/iADLs without loss of balance. The ABC is designed to be used multiple times on a single patient with excellent 4-week test-retest reliability (ICC = 0.85) including item level metrics (ICC = 0.53-0.93).⁶⁴

5.0 Inclusion and Exclusion Criteria/ Study Population

Subjects: We will recruit 72 individuals post-stroke, specifically targeting Veterans, with persistent motoric disability following a clinical diagnosis of stroke, the most recent no less than six months prior to enrollment. Individuals must present with unresolved propulsion asymmetry ($Pp \leq 0.47$ or ≥ 0.53). Subjects will be aged 25 to 75 years to control for the effects of advanced age on the ability to maintain the effects of motor adaptation training.⁶⁶ Participants may be of either gender and will be of diverse ethnic background representing the community. We will also perform a battery of clinical assessments to evaluate degree of function and disability.

Inclusion criteria: 1) 25-75 years of age, 2) stroke \geq 6 months, 3) residual paresis in the lower extremity (Fugl-Meyer LE motor score <34), 4) ability to walk without assistance at speeds ranging from 0.2 – 1.0 m/s (with a support harness for biomechanical testing); 5) $Pp \leq 0.47$ or ≥ 0.53 ; 6) Ability to walk on a treadmill without orthotic or assistive device using overhead harness system; 7) provision of informed consent, and 8) written approval from the primary physician (see attached sample of Medical Approval Cover Letter).

Exclusion criteria will be: 1) history of congestive heart failure, unstable cardiac arrhythmias, hypertrophic cardiomyopathy, severe aortic stenosis, angina or dyspnea at rest or during ADLs; 2) History of COPD or oxygen dependence; 3) Pre-existing neurological disorders or dementia; 3) History of major head trauma; 5) Legal blindness or severe visual impairment; 6) Severe arthritis or other problems that limit passive ROM; 7) History of DVT or pulmonary embolism within 6 months; or 8) Severe hypertension with systolic >200 mmHg and diastolic >110 mmHg at rest.

Statement of Inclusion of Women and Minorities in Research: This research will include women and minorities to the extent reflected by composition of the population in Charleston, SC and its surrounding areas. There are no exclusion or inclusion criteria which would exclude or preclude women or minorities from participating in this study.

Targeted/Planned Enrollment Table

TARGETED/PLANNED ENROLLMENT: Number of Subjects			
Ethnic Category	Sex/Gender		
	Females	Males	Total
Hispanic or Latino	5	5	10
Not Hispanic or Latino	31	31	62
Ethnic Category: Total of All Subjects *	36	36	72
Racial Categories			
American Indian/Alaska Native	0	0	0
Asian	2	2	4
Native Hawaiian or Other Pacific Islander	0	0	0
Black or African American	16	16	32
White	18	18	36
Racial Categories: Total of All Subjects *	36	36	72

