3.0 Intervention to be studied

Intervention

Personalized Intervention: Each participant will be randomized to receive either INCLINE, DECLINE, or CONTROL training. During training, each participant will be asked to walk without an assistive device or ankle-foot orthosis (although an AirCast will be allowed for medial-lateral stability if necessary). For all INCLINE and DECLINE training, individuals will walk for 20 minutes at a 10-degree treadmill tilt, stopping each five minutes for monitoring of vital signs (see “Vital Sign Monitoring” below). As many subjects post-stroke take a beta blocker or other medications that prevent heart rate and blood pressure increases during exertion, a rating of perceived exertion (RPE, must be below “very hard”) will also be collected and adverse events will be strictly monitored. For DECLINE training, the treadmill will be tilted to 10 degrees with the belt reversed and the participant facing in the opposite direction. While participants will be allowed to support themselves with the use of handrails for balance as required, they will wear a climbing harness attached to an overhead support system to prevent falls and thus minimize handrail use. Our previous work was completed at 8 degrees of tilt (see Preliminary Studies), based on work by Werner et al. demonstrating that 8 degrees was required to improve gait symmetry and hip extension in patients with stroke.⁴⁶ Subsequent reports^{29,47} demonstrate that 10 degrees is equally feasible and offers a more intense training opportunity. Individuals will walk at a speed at least 50% of their current overground SSWS, determined at the beginning of each training week, but training as fast as they feel comfortable up to the overground SSWS. Pilot work demonstrated that individuals are not capable of walking on the INCLINE or DECLINE at the overground SSWS secondary to the increased workload associated with the treadmill tilt. Each INCLINE and DECLINE session will be followed by one 6-minute bout of overground walking training as fast as comfortable for each participant focusing on specific gait details targeted in the INCLINE/DECLINE trials (e.g. increased hip extension, increase paretic leg loading, or improved stance to swing transition).

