Vital Sign Monitoring: For all training groups, criteria for termination of training include subject complaints of shortness of breath, light-headedness, confusion, severe headache, or dyspnea; onset of angina; excessive blood pressure (systolic BP > 200mm Hg, diastolic BP > 110 mm Hg), or drop in systolic BP > 10 mm Hg and inappropriate bradycardia (drop in heart rate > 15 bpm).^{48,49} In addition, we will stop training for a rest break if the RPE exceeds “very hard” (17 on a 6-20 scale).

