[name] has been granted permission to break the blind of the data to ensure that randomization to each group is not harmful to the participants. This plan is thoroughly described in the Research Plan and Human Subjects sections. All serious adverse events will be analyzed by the investigative team and the MUSC Institutional Review Board. Serious adverse events are defined as 1) being unexpected; 2) related to a subject’s participation in research; and 3) that subjects are at greater risk of harm than was previously recognized. If greater than 10% in each cell have a serious adverse event, we will evaluate the circumstances and decide if the event was caused by a particular treatment. If a majority of team or the IRB decides that the adverse event was related to intervention, [name] will stop randomizing that patient profile into that group.

Protection Against Risk: A licensed physical therapist will be present in the building during all treatment sessions. In addition, during all treadmill walking trials, a safety harness will be worn to provide assistance in the event of loss of balance. The research staff will closely monitor the subject to ensure their comfort. Any adverse events will be recorded and monitored as required by our Institutional Review Board. In the event of an adverse medical event, standard facility emergency procedures will be followed and proper personnel notified. The PI on this proposal is a licensed physical therapist with over 22 years of experience in the development and implementation of exercise interventions. On-site medical services will be available in the event of adverse events to the subjects. Subjects will be able to terminate the training or testing sessions at their request at any time without prejudice. Minimization of risk will be accomplished by monitoring vital signs every 5 minutes within prescribed criteria for termination of the training session. We will follow the American College of Sports Medicine criteria for terminating an exercise session which

includes: subject complaints of light-headedness, confusion, or dyspnea; onset of angina; excessive blood pressure changes (systolic BP greater than 220 mmHg, diastolic BP greater than 110 mmHg); and inappropriate bradycardia (drop in heart rate >10 beats per minute).

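### Exclusion 8 applies only if both resting blood-pressure limits are exceeded, and the two lists of session-stopping limits contradict each other

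*Combined protocol and SAP*

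**What the plan says.** Three places in the combined protocol and SAP set blood-pressure or heart-rate limits.

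- **Section 5.0, exclusion criterion 8** (resting, at entry): severe hypertension, given as "systolic >200 mmHg and diastolic >110 mmHg at rest". The only other entry safeguard that bears on this is inclusion criterion 8, "written approval from the primary physician", for which the text gives no blood-pressure figure.
- **Section 3.0, Vital Sign Monitoring** (every training group): stop for "excessive blood pressure (systolic BP > 200mm Hg, diastolic BP > 110 mm Hg"), or for "drop in systolic BP > 10 mm Hg and inappropriate bradycardia (drop in heart rate > 15 bpm"). Vital signs are taken every five minutes.
- **Section 13.0, Protection Against Risk** (ending an exercise session, following American College of Sports Medicine criteria): "systolic BP greater than 220 mmHg, diastolic BP greater than 110 mmHg); and inappropriate bradycardia (drop in heart rate >10 beats per minute").

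Section 3.0 also sets a perceived-exertion limit, in two forms. The intervention paragraph asks for "a rating of perceived exertion (RPE, must be below" the very-hard level. The monitoring paragraph, which puts that level at 17 on the 6 to 20 scale, says "we will stop training for a rest break if the RPE exceeds" it.

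**The concern.** Two things look wrong. First, the entry rule is looser than the stopping rules. Someone can be enrolled whose resting pressure already meets a limit at which the protocol would end a session. Second, the two stopping lists cover the same sessions but give different numbers, so staff working from Section 3.0 and staff working from Section 13.0 could act differently on the same reading.

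This is a matter of participant safety. Section 13.0 presents vital-sign checks against prescribed stopping limits as the means of minimizing risk. The participants are stroke survivors walking 20 minutes on a tilted or level treadmill, and Section 3.0 notes that many take drugs that blunt the heart-rate and blood-pressure response to exertion.

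**Working it through.** No figure in the plan needs to be reproduced. The check is to write each rule as a logical condition and apply it to specific readings (SBP = systolic, DBP = diastolic, in mmHg).

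- Exclusion 8: excluded if SBP > 200 **and** DBP > 110.
- Section 3.0: stop if SBP > 200 **or** DBP > 110, or if (systolic drop > 10 **and** heart-rate drop > 15 bpm), read literally.
- Section 13.0: stop if SBP > 220 **or** DBP > 110, or if heart-rate drop > 10 bpm.

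**Entry against stopping**

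| Resting reading | Exclusion 8 | Section 3.0 limit | Section 13.0 limit |
|---|---|---|---|
| 190/115 | not excluded (190 is not > 200) | exceeded (115 > 110) | exceeded (115 > 110) |
| 210/100 | not excluded (100 is not > 110) | exceeded (210 > 200) | not exceeded (210 is not > 220) |

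With *or* in exclusion 8, both readings would be excluded.

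**Section 3.0 against Section 13.0, during a session**

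| Reading | Section 3.0 | Section 13.0 |
|---|---|---|
| 210/100 | stop | limit not met |
| Heart-rate drop of 12 bpm | limit not met | stop |
| Heart-rate drop of 20 bpm, no systolic drop | limit not met on the literal wording | stop |

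The first two rows are plain numeric conflicts. In whole units they cover systolic 201 to 220 with diastolic at or below 110, and heart-rate drops of 11 to 15 bpm. The heart-rate conflict remains however the *and* in Section 3.0 is read, because 11 to 15 is not above 15. The third row depends on reading that *and* as requiring both drops. Section 3.0 also has a systolic-drop criterion that Section 13.0 lacks.

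The diastolic limit is the same in both lists. On systolic pressure Section 3.0 is stricter; on heart-rate drop Section 13.0 is stricter. Choosing one existing list as the safer of the two therefore does not settle the matter.

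**Perceived exertion.** A rating of exactly 17 is not below 17, so it breaches the first statement. It does not exceed 17, so it does not trigger the rest break. The gap is one scale value, and only a rest break is at stake.

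**The case against.** The strongest reply is that this is loose drafting. Exclusion 8 uses the same 200 and 110 as Section 3.0, so an either-limit rule was probably meant, and the exclusion list is carelessly edited elsewhere (two items are numbered 3). The 20 bpm example rests on a strict reading of one conjunction. Both stopping lists are introduced as inclusive rather than exhaustive, and neither tells staff to continue below its values. A team that honours the whole protocol would stop when either list is met, which already gives 200, 110 and 10 bpm. A person enrolled at 190/115 would still need physician approval and, if the reading persisted, would be stopped at the first five-minute check.

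Much of this is fair. The intent behind exclusion 8 probably was *or*, the literal-reading example is the weakest of those shown, and the perceived-exertion gap is minor. The exposure at 190/115 is limited by the five-minute checks.

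The core still stands. No section corrects the *and* in exclusion 8, and the text states no blood-pressure bar to be met before walking starts. The physician's approval carries no stated threshold. Obeying both lists at once is a sensible inference, but the protocol does not state it, and it leads to the same limits proposed below. The systolic and heart-rate conflicts do not depend on how any conjunction is read.

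**Conclusion.** The concern holds. As written, exclusion 8 admits a person at 190/115 at rest who is already over the diastolic stopping limit in both lists; admitted here means not excluded by that criterion. The two lists conflict for systolic readings of 201 to 220 mmHg and for heart-rate drops of 11 to 15 bpm, and no text says which list governs.

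The entry point assumes that exclusion 8 is applied literally. The risk of different action in a session assumes that some staff work from one section without the other. The documents give no frequency for any of these readings, so the number of participants or sessions affected cannot be estimated. Endpoints and analysis are not touched. The wording should be corrected because these limits are the protocol's stated safeguard; the point does not undermine the design.

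**What to change.** 1. In exclusion criterion 8, replace *and* with *or*, so that either resting limit excludes.
2. Write one list of session-stopping limits and use it in both Section 3.0 and Section 13.0. State the systolic drop and the heart-rate drop as separate criteria if that is the intention. Unless the sponsor's clinicians decide otherwise, the stricter value of each pair is a safe default: systolic above 200 mmHg, diastolic above 110 mmHg, heart-rate drop above 10 bpm. Which heart-rate limit is right is a clinical judgement that the documents cannot settle.
3. As a minor tidy-up, call the rest break at a perceived exertion of 17 or above, to match the requirement to stay below that level.

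The cost is protocol wording, possibly a few more screen failures and, with the stricter limits, some more stopped sessions and rest breaks.

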6.0 Number of Subjects

Sample Size Determination and Statistical Approach: A total of 72 individuals post-stroke will be recruited for this study. We are assuming an attrition rate of 20% resulting in a final sample size of 60 for statistical analyses, ideally 10 in each combination of baseline group (low and high Pp) and intervention (INCLINE, DECLINE, and CONTROL training). 10% is consistent with attrition rates from previous trials of locomotor rehabilitation conducted by our group,⁴³ but we have chosen a more conservative rate of 20% based on the novelty and intensity of the intervention. There will be two strata of 30 individuals each with baseline low Pp and high Pp, respectively. From those strata, using block randomization, the subjects will be equally randomized into the INCLINE, DECLINE, and CONTROL training (10 in each training cell).

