Sample Size Determination and Statistical Approach: A total of 72 individuals post-stroke will be recruited for this study. We are assuming an attrition rate of 20% resulting in a final sample size of 60 for statistical analyses, ideally 10 in each combination of baseline group (low and high Pp) and intervention (INCLINE, DECLINE, and CONTROL training). 10% is consistent with attrition rates from previous trials of locomotor rehabilitation conducted by our group,⁴³ but we have chosen a more conservative rate of 20% based on the novelty and intensity of the intervention. There will be two strata of 30 individuals each with baseline low Pp and high Pp, respectively. From those strata, using block randomization, the subjects will be equally randomized into the INCLINE, DECLINE, and CONTROL training (10 in each training cell). The power analysis was based on our pilot training data for INCLINE and DECLINE combined compared to CONTROL. For the power analysis, we used a repeated measures model with an AR(1) correlation value of 0.45 which we obtained from the pilot data. With an average standard deviation of 0.35 (also obtained from the pilot data) and 80% power, with 10 subjects per group we will be able to detect a difference of at least 0.20 between the intervention groups and CONTROL group. A log transformation was applied to achieve normality. Also, we will longitudinally evaluate speed at each session. We will therefore conduct a repeated measures 2-way ANOVA and test the relevant hypotheses using contrasts in a Bonferroni post-hoc analysis. We will include an adjustment for baseline Pp group, intervention group, time, and their interactions. Depending on the within subject correlation across time (which we anticipate to be high) this could also provide additional power. Therefore, in a secondary analysis we will be able to examine several covariates, including the sub-types mentioned above. For each Aim, each variable will be assessed utilizing a repeated measures analysis of variance (baseline Pp, group and time) to evaluate the interaction between baseline Pp, group and time as well as the main effects of treatment for each group and group assignment at each time point. Since pilot data required a log transformation of SSWS, we will assess the final SSWS outcome for normality and perform a transformation if necessary. All power estimates were conducted by a biostatistician ([name]) using PASS 2008 (NCSS, Kaysville, Utah). Spaghetti plots and descriptive statistics regarding HR, BP, and RPE responses to INCLINE and DECLINE training will be reported prior to formal analyses. Patterns of attrition between the 2 groups will also be compared.

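### The plan does not protect its comparisons with CONTROL against selective loss of participants after randomization

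*Combined protocol and SAP*

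**What the plan says.** Section 6.0, repeated in Section 11.0 under the sample size and statistical approach text, sets recruitment: "A total of 72 individuals post-stroke will be recruited for this study". It then says "We are assuming an attrition rate of 20% resulting in a final sample size of 60 for statistical analyses", with 10 intended in each of the six cells formed by baseline Pp and intervention. On the rate, it reports that "10% is consistent with attrition rates from previous trials of locomotor rehabilitation conducted by our group", but "we have chosen a more conservative rate of 20% based on the novelty and intensity of the intervention". The same paragraph describes two strata of 30, randomized equally to 10 per cell.

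The entry criterion in Section 5.0 is "Ability to walk on a treadmill without orthotic or assistive device using overhead harness system"; it names no slope. INCLINE and DECLINE train on a tilted treadmill (Section 3.0). CONTROL walks on a flat treadmill at SSWS (Section 10.0). Section 3.0 adds: "Pilot work demonstrated that individuals are not capable of walking on the INCLINE or DECLINE at the overground SSWS secondary to the increased workload".

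Section 11.0 specifies a repeated measures ANOVA on baseline Pp, group and time, and says "Also, we will longitudinally evaluate speed at each session". Its only provision on dropout is that attrition patterns will be compared between two groups. No section names an analysis population, a missing-data method, or what happens to the assessments of someone who stops training.

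**The concern.** A person can leave because of an intervention's intensity only after being assigned to it, so the reason given for the extra attrition points to loss after randomization. The added workload that the protocol describes is that of the slope. If people who tolerate slope poorly leave INCLINE and DECLINE more often than others leave CONTROL, and if they would have gained less, a comparison of those who remain favours the sloped arms.

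All three aims include a comparison of personalized training with control, and personalized training is always sloped. SSWS, Pp symmetry and response rate would then tend to move in the same direction. Response rate is directly exposed, because a person who leaves also leaves the denominator.

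The plan has no defence against this. The attrition check is descriptive. Its wording follows a sentence about INCLINE and DECLINE, so it may omit CONTROL, the arm that matters most here.

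**Working it through.** **Inputs from the documents.** 72 recruited, 60 for analysis, stated attrition 20%, earlier attrition 10% (Section 6.0); three equal arms, so 24 per arm if 72 are randomized; SD 0.35 and detectable difference 0.20 (Section 11.0).

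**Assumed, not in the documents.** All 72 are randomized; CONTROL loses 10%; in every arm those lost are the lowest on a normally distributed tolerance score; that score correlates r with gain; the plan's SD of 0.35 applies to the outcome compared.

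**Step 1: the plan's own attrition figure.** 72 − 60 = 12 and 12/72 = 16.7%, not 20%. The 72 is obtained as 60 × 1.2. A true 20% loss would need 60/0.8 = 75 recruits, and 72 × 0.8 = 57.6. The illustration uses the 12 losses implied by the plan's two sample sizes.

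**Step 2: loss by arm.** CONTROL: 0.10 × 24 = 2.4. INCLINE and DECLINE together: (12 − 2.4)/48 = 9.6/48 = 20%.

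**Step 3: shift in the mean of those who remain.** After losing the lowest fraction p of a normal distribution, the remaining mean rises by φ(z_p)/(1 − p) SD.
- Sloped arms, p = 0.20: 0.280/0.80 = 0.350 SD.
- CONTROL, p = 0.10: 0.1755/0.90 = 0.195 SD.
- Difference: 0.350 − 0.195 = 0.155 SD.

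**Step 4: scale by r and SD 0.35, and compare with 0.20.**

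| r | Shift | Share of 0.20 |
|---|---|---|
| 1 | 0.155 × 0.35 = 0.054 | 27% |
| 0.5 | 0.155 × 0.5 × 0.35 = 0.027 | 14% |
| 0.3 | 0.155 × 0.3 × 0.35 = 0.016 | 8% |

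If all arms lose the same fraction in the same way, the difference is zero. A CONTROL loss below 10% would enlarge it. Section 11.0 mentions a log transformation without saying whether 0.35 and 0.20 are on that scale; the shares hold if both are on the same scale.

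**Step 5: response rate.** If everyone lost is a true non-responder, the rate among those who remain is the true rate divided by 0.80 in the sloped arms and by 0.90 in CONTROL. The ratio of response rates is then overstated by 0.90/0.80 = 1.125, or 12.5%.

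**The case against.** Four stronger readings are tempting, and the documents do not support them.

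- **That the sloped arms are enriched.** No section gives loss by arm, and the target of 10 in every cell, CONTROL included, implies equal loss. The stated reason refers to the intervention without naming an arm. The pilot remark explains why slower training speeds are allowed and does not report dropout. Sloped training may run at as little as 50% of SSWS, handrails are permitted (Section 3.0), and up to 20% body weight support is allowed (Section 13.0). These provisions may limit slope-related loss. CONTROL walks at full SSWS.
- **That only completers will be analysed.** The 60 comes from a sample-size sentence, not an analysis-set definition. With SSWS recorded around every session, a repeated measures analysis could retain partial data. However, the plan does not say that it will, and classical ANOVA would not.
- **That the sloped arms lose 25%.** Applying 20% to 72 gives 14.4 losses, a sloped loss of (14.4 − 2.4)/48 = 25%, and shifts of 0.080 or 0.040. That leaves 57.6, not the 60 the plan carries forward.
- **That the personalized versus non-personalized contrast is biased.** Each of those groups mixes INCLINE and DECLINE, so general slope intolerance largely cancels. The contrast is affected only if tolerance depends on Pp stratum, on which the documents are silent.

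In addition, the two strata of 30, read literally, mean that 60 are randomized and 12 are lost beforehand. No loss after randomization would then follow from these figures. The reason given for the attrition points the other way, so the text is ambiguous. The lack of a slope test at entry is a fact about the design, not in itself an error.

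These objections reduce the claim from a demonstrated bias to an unprotected risk. They do not supply the missing analysis population, missing-data method or follow-up rule.

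**Conclusion.** The concern holds as a gap in the plan. Extra attrition is expected for a reason tied to treatment, and nothing preserves the randomized comparison with CONTROL if that loss is uneven. Under the stated assumptions the shift is 0.027 to 0.054 for correlations of 0.5 to 1, or 14% to 27% of the difference the trial is sized to detect. It is smaller at lower correlations and zero if loss is equal across arms. The CONTROL rate, the correlation and its direction are all assumed; nothing in the documents shows that people who tolerate slope poorly gain least. The correction is worth making because it is cheap and most of the SSWS data it needs are already to be collected.

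**What to change.** - State whether 72 or 60 participants are randomized, and reconcile this with the 20% attrition figure and the two strata of 30.
- Make the primary analysis all randomized participants in the group assigned, fitted as a likelihood-based mixed model. For SSWS, use baseline and every session value up to withdrawal.
- State that stopping training is not leaving the study, and invite these participants to the scheduled post-training and one-month assessments. This matters most for Pp, which has no session-by-session record to draw on.
- Report attrition for all three arms and by Pp stratum, in place of the two-group comparison.
- For Hypothesis 3.1, report the response rate with missing counted as non-response as a sensitivity analysis, alongside a completer analysis. Counting every missing value as non-response is a strong assumption and should not be the primary rule.

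The cost is revised protocol and analysis wording, plus a few already scheduled visits for people who stop training. The estimated effect may be somewhat smaller than among completers. The mixed model does not remove bias from loss that depends on unobserved outcomes, which is why the follow-up visits and sensitivity analyses are needed as well.
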